12.3. Study Documentation and Storage

An eCRF utilizing an Electronic Data Capture (EDC) application will be used for this study.

The Investigator should ensure that all appropriately qualified persons to whom he/she has delegated trial duties are recorded on a Sponsor-approved Delegation of Site Responsibilities Form.

Source documents are original documents, data, and records from which the patient's CRF data are obtained. These include but are not limited to hospital records, clinical and office charts, laboratory and pharmacy records, imaging, and correspondence. In this study, eCRF may not be used as source documents.

The Investigator and Study Center staff are responsible for maintaining a comprehensive and centralized filing system of all study-related (essential) documentation in accordance with ICH GCP, suitable for inspection at any time by representatives from the Sponsor and/or applicable regulatory authorities. Elements should include:

- Patient files containing completed CRFs, informed consents, and supporting copies of source documentation
- Study files containing the protocol with all amendments, Investigator's Brochure, copies of pre-study documentation and all correspondence to and from the IRB and the Sponsor
- If drug supplies are maintained at the Study Center, proof of receipt, Study Drug Product Accountability Record, Return of Study Drug Product for Destruction, final Study Drug product reconciliation, and all drug-related correspondence

In addition, all original source documents supporting entries in the CRFs must be maintained and be readily available.

No study document should be destroyed without prior written agreement between the Sponsor and the Investigator. Should the Investigator wish to assign the study records to another party or move them to another location, he/she must notify the Sponsor.

12.4. Study Monitoring

The Sponsor representative and regulatory authority inspectors are responsible for contacting and visiting the Investigator for the purpose of inspecting the facilities and, upon request, inspecting the various records of the trial (e.g., CRFs and other pertinent data) provided that patient confidentiality is respected.

The Sponsor monitor or designee is responsible for inspecting the CRFs at regular intervals throughout the study to verify adherence to the protocol; completeness, accuracy, and consistency of the data; and adherence to local regulations on the conduct of clinical research. The monitor should have access to patient medical records and other study-related records needed to verify the entries on the CRFs.

The Investigator agrees to cooperate with the monitor to ensure that any problems detected in the course of these monitoring visits, including delays in completing CRFs, are resolved.

In accordance with ICH GCP and the Sponsor's audit plans, this study may be selected for audit by representatives from the Sponsor's Clinical Quality Assurance Department. Inspection of Study Center facilities (e.g., pharmacy, drug storage areas, laboratories) and review of study-related records will occur to evaluate the trial conduct and compliance with the protocol, ICH GCP, and applicable regulatory requirements.

To ensure the quality of clinical data a clinical data management review will be performed on patient data received by the Sponsor. During this review, patient data will be checked for consistency, omissions, and any apparent discrepancies. In addition, the data will be reviewed for adherence to the protocol and GCP. To resolve any questions arising from the clinical data management review process, data queries and/or Study Center notifications will be sent to the Study Center for completion and return to Sponsor.

The Principal Investigator will sign and date the indicated places on the CRF. These signatures will indicate that the Principal Investigator inspected or reviewed the data on the CRF, the data queries, and the Study Center notifications, and agrees with the content.

12.5. Language

Case report forms must be completed in English. Generic names and trade names are acceptable for concomitant medications. Combination medications should be recorded using their trade name.

All written information and other material to be used by patients and investigative staff must use vocabulary and language that are clearly understood.

12.6. Compensation for Injury

The Sponsor maintains appropriate insurance coverage for clinical trials and will follow applicable local compensation laws. Patients will be treated and/or compensated for any study-related illness/injury in accordance with the information provided in the Compensation for Injury section of the Informed Consent document.

APPENDIX A. SCHEDULE OF PROCEDURES

Appendix A Schedule of Procedures

	Scree	n	Treati (12 W		Period										Post-Treatm (13 Weeks)	nent Pe	riod			
Study Week			Wk1	Wk2	Wk3	Wk4	Wk5	Wk6	Wk7	Wk8	Wk9	Wk10	Wk11	Wk12	Wk13	Wk14	Wk16	Wk18	Wk22	Wk25
Study Day	D-42 D-1	to	D1	D8	D15	D22	D29	D36	D43	D50	D5 7	D64	D71	D78	Treatment Early Term ⁹ /D85	D92	D106	D120		PT Early Term ⁹ / D169
Visit Window (Days)	NA		NA	± 2	± 2	± 2	± 2	± 2	± 2	± 2	± 2	± 2	± 2	± 2	± 2	± 2	± 2	± 5	± 5	± 5
Scheduled Visit #	1	2	3	4	5	6	7	8	9	10	11	12	13	14	15	16	17	18	19	20
Option for Home Health Care Visit ¹⁰				X	X	X	X	X	X	X	X	X	X	X ¹⁴		X ¹⁴	X	X	X	
Informed Consent	X																			
Inclusion/Exclusion	X	X	Xa																	
Medical History	X																			
Hydration and Low Sodium Diet Education	X	←	Continuous Counseling & Monitoring																	
CVD Risk Factors	X																			
Body Weight and Height ⁸	X		X												X					X
Physical Exam ¹	X		X												X					X
ECG (12-Lead)	X														X					
EQ-5D-5L, SF-12, POP-HSQ ¹⁵			X						X						X		X			
PGI-S ¹⁵			X												X					
PGI-C ¹⁵															X					
HTN Medication Compliance			X	X	X.	X	X	X	X.	X	X	X	X	X	X	X	X	X	X	X
Vital Signs (clinic) ²	X	X	Xa	Xa	Xª	Xª	Xª	Xª	Xª	Xª	Xª	Xª	Xa	Xa	X	X	X	X	X	X
HIV, Hep B & C	X																			
FSH ³	X																			
Pregnancy Test.4	X																			
Chemistry Panel ^{7, 10}	X		Xª		Xª		Xª		Xª		Xª		Xª		X	X	X	X	X	X
Archived Urine Sample.6	X		Xª				Xª				Xª				X	X	X	X	X	X
TSH, FT3, FT4	X																			
Hematology. ⁷	X		Xª		Xª		Xª		Xª		Xª		Xª		X	X	X	X		X
Urinalysis. ¹⁰	X^{16}		Xª		Xª		Xª		Xª		Xª		Xa		X	X	X	X	X	X

Amendment 4 4 November 2021

Appendix A Schedule of Procedures (Continued)

	Scre	en	Treati (12 W		Period										Post-Treatn (13 Weeks)	nent Pe	riod			
Study Week			Wk1	Wk2	Wk3	Wk4	Wk5	Wk6	Wk7	Wk8	Wk9	Wk10	Wk11	Wk12	Wk13	Wk14	Wk16	Wk18	Wk22	Wk25
Study Day	D-42	to D-1	D1	D8	D15	D22	D29	D36	D43	D50	D5 7	D64	D71	D78	Treatment Early Term ⁹ /D85	D92	D106	D120	D148	PT Early Term ⁹ / D169
Visit Window (Days)	NA		NA	± 2	± 2	± 2	± 2	± 2	± 2	± 2	± 2	± 2	± 2	± 2	± 2	± 2	± 2	± 5	± 5	± 5
Scheduled Visit #	1	2	3	4	5	6	7	8	9	10	11	12	13	14	15	16	17	18	19	20
Option for Home Health Care Visit ¹⁰				X	X	X	X	X	X	X	X	X	X	X ¹⁴		X ¹⁴	X	X	X	
Plasma AGT	X		Xª		Xª		Xª		Xª		X.a		Xª		X	X	X	X	X	X
Exploratory	X		Xª						Xª						X		X	X	X	X
24-hr ABPM		X ¹¹													X ¹³					
Study Drug Administration ¹²			X	X	X	X	X	X	X	X	X	X	X	X						
hs-CRP			Xª												X					X
PT, INR, aPTT	X																			
AEs	X		X	X	X	X	X	X	X	X	X	X	X	X	X	X	X	X	X	X
Concomitant Medications	X		X	X	X	X	X	X	X	X	X	X	X	X	X	X	X	X	X	X
PK Blood Sampling.5			X^b		Xa		Xª		Xª		X.a		Xª	X^b	X	X	X	X	X	X
Anti-drug Antibody (ADA) Testing			Xª		Xa		Xª				X.a				X					X
Archived Serum Sample.6			X		X		X				X		X		X			X		X
Patient Contact	If an medi	in-clinio cations,	e visit o adequa	r Hom te hyd	e Heal	ltheare and lo	visit o w sodi	annot um di	be con	nducte nseling	d, patie g (e.g., v	nt conta video ca	ect is rec ill, text,	quired b email,	y site personi etc.)	nel to as	sess AE	s, conc	omitant	

Note: D = Day, Wk = Week

¹ Full physical exam to be given at Screening and abbreviated physical exam to be given during Treatment and Post-Treatment Period as indicated to assess changes from Screening

² Vital Signs (clinic): Blood pressure (SBP/DPB; sitting), Orthostatic assessment (supine and standing, required at Screening Visit 1), heart rate, respiratory rate, temperature. Vital sign assessments will be reviewed by the study doctor at each visit prior to dosing

Women who are not surgically sterile, and women who require confirmation of menopause at Screening per Inclusion Criterion 3

⁴ Women who are not surgically sterile. Serum test to be done

⁵ Refer to Appendix C for PK sampling schedule

⁶ Stored for follow-up exploration of laboratory findings and/or AEs (e.g., measurement of cytokine and/or chemokine levels, measurement of additional markers of kidney function, measurement of antibodies, etc.) in this or subsequent clinical studies of ISIS 757456

If the platelet value, eGFR, UPCR, potassium, or liver enzyme tests are uninterpretable (e.g., due to clumping, hemolysis or quantity not sufficient) a repeat blood specimen; should be re-drawn as soon as possible (ideally within 7 days either in clinic, by Home Healthcare, or local laboratory) and not meet a stopping rule prior to next dose. If Day 1 results are uninterpretable, Day 8 dosing may proceed, however, an interpretable result is required (and must be reviewed) before study drug dosing on Day 15.

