	• To evaluate the effect of ISIS 757456 on 24-hour ambulatory blood pressure at Study Day 85 in uncontrolled hypertensive patients on ≥ 3 antihypertensive medications	
	• To evaluate the effect of ISIS 757456 on seated automated office SBP at each scheduled visit in uncontrolled hypertensive patients on ≥ 3 antihypertensive medications	
	• To evaluate the effect of ISIS 757456 on seated automated office diastolic blood pressure (DBP) at each scheduled visit in uncontrolled hypertensive patients on ≥ 3 antihypertensive medications	
Exploratory Objectives	• To evaluate the effects of ISIS 757456 administered subcutaneously (SC) (e.g., angiotensin II, renin [Plasma renin activity (PRA); direct renin], urinary AGT) in uncontrolled hypertensive patients on ≥ 3 antihypertensive medications	
	• To evaluate the pharmacokinetics (PK) of ISIS 757456 (as total full length ASO, including fully conjugated, partially conjugated, and unconjugated ISIS 757456) administered SC in uncontrolled hypertensive patients on ≥ 3 antihypertensive medications	
	To evaluate potential PK / pharmacodynamic (PD) correlation with relevant biomarkers and/or clinical endpoints	
Safety Objective	 To evaluate the safety and tolerability of ISIS 757456 in uncontrolled hypertensive patients on ≥ 3 antihypertensive medications To evaluate the effects of ISIS 757456 on patient reported quality of life outcomes 	
Study Design	Randomized, double blind, placebo controlled, multi-center study	
Number of Patients	Approximately 150 patients will be enrolled	

Study Population

Inclusion Criteria

- 1. Must have given written informed consent (signed and dated) and any authorizations required by local law and be able to comply with all study requirements
- 2. Males or females aged 18–80 inclusive and weighing ≥ 50 kg at the time of informed consent
- 3. Satisfy the following:
 - a. Females: must be non-pregnant and non-lactating, and either:
 - i. surgically sterile (e.g., bilateral tubal occlusion, hysterectomy, bilateral salpingectomy, bilateral oophorectomy)
 - ii. post-menopausal (defined as 12 months of spontaneous amenorrhea in females > 55 years of age or, in females ≤ 55 years, 12 months of spontaneous amenorrhea without an alternative medical cause and follicle stimulating hormone (FSH) levels in the postmenopausal range for the laboratory involved)

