5.1. Inclusion Criteria

- 1. Must have given written informed consent (signed and dated) and any authorizations required by local law and be able to comply with all study requirements
- 2. Males or females aged 18–80 inclusive and weighing ≥ 50 kg at the time of informed consent
- 3. Satisfy the following:
 - a. Females: must be non-pregnant and non-lactating, and either:
 - i. surgically sterile (e.g., bilateral tubal occlusion, hysterectomy, bilateral salpingectomy, bilateral oophorectomy) or
 - ii. post-menopausal (defined as 12 months of spontaneous amenorrhea in females > 55 years of age or, in females ≤ 55 years, 12 months of spontaneous amenorrhea without an alternative medical cause and follicle stimulating hormone (FSH) levels in the postmenopausal range for the laboratory involved)
 - b. Males must be abstinent*, surgically sterile (vasectomy with negative semen analysis at follow-up) or if engaged in sexual relations with a woman of childbearing potential (WOCBP), a highly effective contraceptive method must be used (refer to Section 6.4.1) from the time of signing the informed consent form until at least 20 weeks after the last dose of Study Drug (ISIS 757456 or placebo) or abstinent*
 - * Abstinence is only acceptable as true abstinence, i.e., when this is in line with the preferred and usual lifestyle of the patient. Periodic abstinence (e.g., calendar, ovulation, symptothermal, post-ovulation methods), declaration of abstinence for the duration of a trial and withdrawal are not acceptable methods of contraception.
- 4. body mass index (BMI) $\leq 45.0 \text{ kg/m}^2$
- 5. Brachial circumference \geq 22 and \leq 43 cm (8.7 and 16.9 inches)

- 6. At Screening, the patient must have been on a stable, maximally tolerated regimen (per Investigator judgement) of 3 or more antihypertensive medications for at least 1 month prior to screening and will be required to maintain this regimen throughout the Study. The combination of antihypertensive medications must be in the following categories:
 - a. angiotensin-converting enzyme inhibitor (ACEi) or angiotensin II receptor blocker (ARB)
 - b. beta blocker
 - c. calcium channel blocker
 - d. diuretic
 - e. alpha-1 blocker
 - f. centrally acting sympatholytic agent
 - g. direct acting vasodilators (e.g., hydralazine)

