6.4. Restriction on the Lifestyle of Patients

6.4.1. Contraception Requirements

All male and female patients must refrain from sperm/egg donation from the time of signing the informed consent until at least 20 weeks after the patient's last dose of study treatment.

Males must be abstinent[†], or if engaged in sexual relations with a woman of childbearing potential, highly effective contraception must be used from the time of signing the informed consent until at least 20 weeks after the patient's last dose of study treatment.

For the purposes of this study, WOCBP are defined as any female who has experienced menarche, and who does not meet one of the following conditions:

- Postmenopausal: 12 months of spontaneous amenorrhea in females > 55 years of age
 or, in females ≤ 55 years, 12 months of spontaneous amenorrhea without an
 alternative medical cause and FSH levels in the postmenopausal range for the
 laboratory involved
- 6 weeks after surgical bilateral oophorectomy with or without hysterectomy
- Post-hysterectomy

[figure not shown]
For the purposes of the study, highly effective contraception is defined as follows:

- For males: surgical sterilization (vasectomy with negative semen analysis at follow-up), a surgically sterile non-pregnant female partner, or the non-pregnant female partner of WOCBP uses a highly effective contraceptive method (defined below)
- For female partners of male subjects: surgical sterilization (e.g., bilateral tubal occlusion, hysterectomy, bilateral salpingectomy, bilateral oophorectomy), hormonal contraception associated with inhibition of ovulation (combined estrogen and progestogen containing, or progestogen-only), intrauterine contraception device or intrauterine hormone-releasing system (IUS).

Male patients with partners that are pregnant must use condoms as barrier method to ensure that the fetus is not exposed to the Study Drug.

†Note: Abstinence (i.e., refraining from heterosexual intercourse throughout the duration of study participation) is only acceptable as true abstinence, i.e., when this is in line with the preferred and usual lifestyle of the patient. Periodic abstinence (e.g., calendar, ovulation, symptothermal, post-ovulation methods), declaration of abstinence for the duration of a trial and withdrawal are not acceptable methods of contraception.

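### The one scheduled pregnancy test skips pre-menopausal women who are eligible only through tubal occlusion or salpingectomy; rewording one Appendix A footnote would close the gap (minor, patient safety)

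*Combined protocol and SAP*

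**What the plan says.** Inclusion criterion 3a (Protocol Synopsis and Section 5.1) opens with "Females: must be non-pregnant and non-lactating, and either" and then gives two routes. The first is being "surgically sterile (e.g., bilateral tubal occlusion, hysterectomy, bilateral salpingectomy, bilateral oophorectomy"), with no condition on age or menopausal status. The second is being post-menopausal, defined by a year without periods, plus a confirmatory FSH level and no other medical cause in women aged 55 or under.

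The row "Pregnancy Test.4" in the Appendix A schedule is marked once, at Screening Visit 1. Its footnote reads "Women who are not surgically sterile. Serum test to be done". The FSH footnote beside it also turns on surgical sterility: "Women who are not surgically sterile, and women who require confirmation of menopause at Screening per Inclusion Criterion 3".

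Section 6.4.1 defines childbearing potential separately: "For the purposes of this study, WOCBP are defined as any female who has experienced menarche" and who meets none of three exempting conditions. These are being post-menopausal, being post-hysterectomy, or being "6 weeks after surgical bilateral oophorectomy with or without hysterectomy". Tubal occlusion and salpingectomy are not among them.

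**The concern.** Non-pregnancy is a requirement in its own right under 3a, on top of either route to eligibility. The only scheduled test of it goes to one route and not the other. Among the women left out are those who still have a uterus and ovaries and have not reached menopause.

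The protocol takes fetal exposure seriously elsewhere. Section 6.4.1 requires condoms for men with pregnant partners so that the fetus is not exposed. Section 8.8 makes pregnancy a reason for permanent discontinuation. Section 2.3.4 puts the elimination half-life at about 2 to 4 weeks, so stopping the drug after a pregnancy is recognised would not end exposure promptly. A check before the first dose therefore has some value, and for this group no scheduled test provides one.

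**Working it through.** No figure in the plan needs to be reproduced. The check crosses three rules: who is eligible (3a), who is tested (footnote 4), and whom Section 6.4.1 exempts from childbearing potential. The last two columns count pregnancy tests in Appendix A over its 20 scheduled visits, under the present footnote and under the wording proposed below.

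| Woman eligible under 3a | Exempt under 6.4.1? | Tests now | Tests if reworded |
|---|---|---|---|
| Post-menopausal, no sterilizing operation | Yes | 1 | 1 |
| Hysterectomy | Yes | 0 | 0 |
| Bilateral oophorectomy at least 6 weeks earlier | Yes | 0 | 0 |
| Post-menopausal, tubal occlusion or salpingectomy only | Yes | 0 | 1 |
| Pre-menopausal, tubal occlusion only | No | 0 | 1 |
| Pre-menopausal, bilateral salpingectomy only | No | 0 | 1 |

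Step by step:

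1. 3a admits 2 groups, surgically sterile and post-menopausal. Footnote 4 removes the surgically sterile. Among eligible women that leaves 1 of 2 groups with a test: post-menopausal women without a sterilizing operation.
2. The two pre-menopausal rows are eligible, untested and outside the 6.4.1 exemptions. No other row has all three properties.
3. One edge case lies outside the table. A woman less than 6 weeks after bilateral oophorectomy is also not covered by the oophorectomy exemption and would go from 0 to 1 test, unless she has also had a hysterectomy. Exclusion criterion 1 gives major surgery within 2 months of Screening as an example of a disqualifying history, so she should rarely appear.
4. The operations in 3a are introduced as examples. An exception-based footnote also covers any other operation accepted as sterilizing that leaves the uterus and ovaries in place.
5. Timing: 1 of the 20 visits carries the test. Screening may start on Study Day -42 (Section 3.4.1), so the result can be up to 42 days, or 42 / 7 = 6 weeks, old at first dose.

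No expected number of pregnancies is given. The documents state neither how many such women will enrol nor a pregnancy rate after these operations.

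**The case against.** The strongest answer is that the plan applies one rule consistently. Footnote 4 and 3a use the same term. Section 6.4.1 itself counts tubal occlusion and salpingectomy as surgical sterilization when it lists highly effective methods for male patients' partners. A reader might infer from the 6.4.1 definition that the protocol contradicts itself by enrolling women of childbearing potential untested. The documents do not support that. The definition is put to use only for men "engaged in sexual relations with a woman of childbearing potential, highly effective contraception must be used", and 3a never applies it to enrolled women. It serves here only as the protocol's own description of who could still conceive.

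A reader might also infer that the test is aimed at the wrong women. That goes too far as well. The test is done before eligibility is settled. A non-sterile woman qualifies through a history of absent periods, which pregnancy can mimic, whereas surgical sterility rests on a past operation. Testing the first route is sensible and should be kept.

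Nor is the criterion otherwise unchecked. Eligibility is reviewed at Visit 1, Visit 2 and before dosing on Day 1. Medical history is taken at Visit 1, physical examination is done at Visit 1 and Day 1, and the investigator verifies eligibility before randomization (Section 4.2). Section 9.4.3.6 provides for follow-up of any pregnancy in a patient.

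All of this stands, and it limits the importance of the point. It does not supply a scheduled pre-dose test for the skipped group. The plan gives no reason for testing post-menopausal women at that visit while omitting women who have a uterus, ovaries and no menopause.

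**Conclusion.** This is a cheap patient-safety improvement, minor in grade, and not an error in the plan. By the Appendix A schedule, pre-menopausal women who qualify only through tubal occlusion or salpingectomy have 0 scheduled pregnancy tests, and post-menopausal women without a sterilizing operation have 1.

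The absolute risk is low, since the protocol itself treats these operations as sterilization, and it cannot be computed. Nothing in the documents shows that a pregnant woman would be dosed. No endpoint, sample size, power figure or analysis changes.

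The conclusion assumes that footnote 4 uses surgical sterility in the sense given in 3a. It also assumes that Appendix B does not specify a further pregnancy test. Its analyte table was not readable in the copy available, so the count of 0 is established for Appendix A only.

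**What to change.** Reword Appendix A footnote 4 to: *All women except those post-hysterectomy or at least 6 weeks after bilateral oophorectomy. Serum test to be done.* Leave Inclusion criterion 3a as it is. The two exceptions match the surgical exemptions in Section 6.4.1, and post-menopausal women tested now stay tested. Check Appendix B at the same time so that the two appendices agree.

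The cost is one serum assay for each added woman, on blood already drawn at Visit 1 (Section 6.1.1). The added women include some with little to gain: post-menopausal women with earlier tubal surgery, and any woman less than 6 weeks after bilateral oophorectomy. Eligibility, visits, sample size and analysis are unchanged. The benefit is limited to a pregnancy already detectable at Screening; one that begins between Screening and Day 1, or during treatment, would still not be found by this test.
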